13.2 Serious Adverse Events

An AE is considered "serious" if in the opinion of the investigator it is one of the following outcomes:

- Fatal
- Life-threatening
- Constitutes a congenital anomaly or birth defect
- A medically significant condition (defined as an event that compromises subject safety or may require
- medical or surgical intervention to prevent one of the three outcomes above).
- Requires inpatient hospitalization or prolongation of existing hospitalization
- Results in persistent or significant incapacity or substantial disruption to conduct normal life functions.

13.2.1 Reporting of SAEs

All SAEs should be reported immediately to [name] ([contact]) or her designee [contact]) and to the FDA. Fatal or life-threatening, unexpected adverse events will be reported to the FDA by telephone, facsimile, or in writing as soon as possible, but no later than 7 calendar days after first knowledge by the sponsor followed by as complete a report as possible within 8 additional calendar days. Serious, unexpected adverse events that are not fatal or life-threatening will be reported to the FDA by telephone, facsimile, or in writing as soon as possible, but no later than 15 calendar days after first knowledge by the sponsor.

All adverse events that are considered serious, unanticipated, and related or possibly related to the research (as defined by 21CFR312.32[a]) will be reported to the Duke University Medical Center IRB and the FDA using the appropriate SAE reporting process. At the time of the annual progress report to the Duke University Medical Center IRB and the FDA, a summary of the overall toxicity experience will be provided.

13.3 Emergency Unblinding of Investigational Treatment

In the case of an allergic reaction following the pre-conditioning part of the study, the research nurse administering the study drug(s) will alert the PI (or her designate) for PI notification and approval to initiate unblinding and the ICS will be contacted to obtain information on the pre-conditioning regimen the subject received. [name] (study PI) can be reached at [contact] during regular business hours and at [contact] (or [contact] for page office if designate) after hours and on weekends and holidays. The ICS Pharmacy can be reached at [contact].

13.4 Safety Oversight Committee (SOC)

The DCI SOC is responsible for annual data and safety monitoring of DUHS sponsor-investigator phase I and II, therapeutic interventional studies that do not have an independent DSMB. The primary focus of the SOC is review of safety data, toxicities and new information that may affect subject safety or efficacy. Annual safety reviews includes but may not be limited to review of safety data, enrollment status, stopping rules if applicable, accrual, toxicities, reference literature, and interim analyses as provided by the sponsor-investigator. The SOC in concert with the DCI Monitoring Team (see Section 14.1 for Monitoring Team description) oversees the conduct of DUHS cancer-related, sponsor-investigator therapeutic intervention and prevention intervention studies that do not have an external monitoring plan, ensuring subject

safety and that the protocol is conducted, recorded and reported in accordance with the protocol, SOPs, GCP, and applicable regulatory requirements.

13.5 External Data and Safety Monitoring Board (DSMB)

The Principal Investigator and Sub-Investigators must comply with applicable federal, state, and local regulations regarding reporting and disclosure of conflict of interest. Conflicts of interest may arise from situations in which financial or other personal considerations have the potential to compromise or bias professional judgment and objectivity. Conflicts of interest include but are not limited to royalty or consulting fees, speaking honoraria, advisory board appointments, publicly-traded or privately-held equities, stock options, intellectual property, and gifts.

The Duke University School of Medicine's RIO reviews and manages research-related conflicts of interest. The Principal Investigator and Sub-Investigators must report conflicts of interest annually and within 10 days of a change in status, and when applicable, must have a documented management plan that is developed in conjunction with the Duke RIO and approved by the IRB/IEC.

Due to potential for COI in relation to proprietary interest in the pp65CMV DC vaccine, a Data Safety and Monitoring Board (DSMBplus) has been established. Please see Appendix – Section 18.6 for detail on the Duke PRTBTC DSMBplus Charter.

14 QUALITY CONTROL AND QUALITY ASSURANCE

14.1 Monitoring

The DCI Monitoring Team will conduct monitoring visits to ensure subject safety and to ensure that the protocol is conducted, recorded, and reported in accordance with the protocol, standard operating procedures, good clinical practice, and applicable regulatory requirements. As specified in the DCI Data and Safety Monitoring Plan, the DCI Monitoring Team will conduct routine monitoring after the third subject is enrolled, followed by annual monitoring of 1 – 3 subjects until the study is closed to enrollment and subjects are no longer receiving study interventions that are more than minimal risk.

Additional monitoring may be prompted by findings from monitoring visits, unexpected frequency of serious and/or unexpected toxicities, or other concerns and may be initiated upon request of DUHS and DCI leadership, the DCI Cancer Protocol Committee, the SOC, the sponsor, the Principal Investigator, or the IRB. All study documents must be made available upon request to the DCI Monitoring Team and other authorized regulatory authorities, including but not limited to the National Institute of Health, National Cancer Institute, and the FDA. Every reasonable effort will be made to maintain confidentiality during study monitoring.

14.2 Audits

The Duke School of Medicine CTQA office may conduct audits to evaluate compliance with the protocol and the principles of GCP. The PI agrees to allow the CTQA auditor(s) direct access to

all relevant documents and to allocate his/her time and the time of the study team to the CTQA auditor(s) in order to discuss findings and any relevant issues.

CTQA audits are designed to protect the rights and well-being of human research subjects. CTQA audits may be routine or directed (for cause). Routine audits are selected based upon risk metrics generally geared towards high subject enrollment, studies with limited oversight or monitoring, Investigator initiated Investigational Drugs or Devices, federally-funded studies, high degree of risk (based upon adverse events, type of study, or vulnerable populations), Phase I studies, or studies that involve Medicare populations. Directed audits occur at the directive of the IRB or an authorized Institutional Official.

CTQA audits examine research studies/clinical trials methodology, processes and systems to assess whether the research is conducted according to the protocol approved by the DUHS IRB. The primary purpose of the audit/review is to verify that the standards for safety of human subjects in clinical trials and the quality of data produced by the clinical trial research are met. The audit/review will serve as a quality assurance measure, internal to the institution. Additional goals of such audits are to detect both random and systemic errors occurring during the conduct of clinical research and to emphasize “best practices” in the research/clinical trials environment.

14.3 Data Management and Processing

14.3.1 Study Documentation

Study documentation includes but is not limited to source documents, case report forms, monitoring logs, appointment schedules, study team correspondence with sponsors or regulatory bodies/committees, and regulatory documents that can be found in the DCI-mandated “Regulatory Binder”, which includes but is not limited to signed protocol and amendments, approved and signed informed consent forms, FDA Form 1572, CAP and CLIA laboratory certifications, and clinical supplies receipts and distribution records.

Source documents are original records that contain source data, which is all information in original records of clinical findings, observations, or other activities in a clinical trial necessary for the reconstruction and evaluation of the trial. Source documents include but are not limited to hospital records, clinical and office charts, laboratory notes, memoranda, subjects’ diaries or evaluation checklists, pharmacy dispensing records, recorded data from automated instruments, copies or transcriptions certified after verification as being accurate copies, microfiches, photographic negatives, microfilm or magnetic media, x-rays, subject files, and records kept at the pharmacy, at the laboratories and at medico-technical departments involved in the clinical trial. When possible, the original record should be retained as the source document. However, a photocopy is acceptable provided that it is a clear, legible, and an exact duplication of the original document.

14.3.2 Data Management

The subject’s medical records will be the primary source document for the study. Source documents include all information in original records and certified copies of original records of clinical findings, observations, or other activities in a clinical investigation used for

reconstructing and evaluating the investigation.¹³ Source documentations may also include paper eligibility checklists, data flowsheets, patient reported outcomes and other paper documents. The PI, study coordinator, study research nurse, data management team and all associated study key personnel, are permitted to make entries, changes, or corrections in the source documents or database per the study delegation of authority log.

Errors on the source documents will be crossed out with a single line, and this line will not obscure the original entry. Changes or corrections will be dated, signed, initialed, and explained (if necessary). Database changes will be tracked via electronic trail automatically.

14.3.3 Data Management Procedures and Data Verification

The DCI IT Shared Resource has developed Title 21 CFR Part 11 compliant databases for cancer clinical trials. DCI IT has extensive expertise in database quality assurance, data standards, and use of caBIG tools to support cancer researchers.

Data queries will be generated automatically by the eCRF system. These data queries signify the presence of data inconsistencies. The study and data management team will cross-reference the data to verify accuracy. Missing or implausible data will be highlighted for the PI requiring appropriate responses (i.e., confirmation of data, correction of data, completion or confirmation that data is not available, etc.).

The database will be reviewed and discussed prior to database closure, and will be closed only after resolution of all remaining queries.

14.3.4 Coding

All medical terms will be coded using CTCAE (version 4).

14.3.5 Study Closure

Following completion of the studies, the PI will be responsible for ensuring the following activities:

- Data clarification and/or resolution
- Accounting, reconciliation, and destruction/return of used and unused study drugs
- Review of site study records for completeness
- Shipment of all remaining laboratory samples to the designated laboratories

15 STATISTICAL METHODS AND DATA ANALYSIS

All statistical analysis will be performed under the direction of the statistician designated in key personnel. Any data analysis carried out independently by the investigator must be approved by the statistician before publication or presentation.

¹³ In 21 CFR 312.62(b), reference is made to records that are part of case histories as “supporting data;” the ICH guidance for industry *E6 Good Clinical Practice: Consolidated Guidance* (the ICH E6 guidance) (available at <http://www.fda.gov/Drugs/GuidanceComplianceRegulatoryInformation/Guidances/default.htm>) uses the term “source data/documents.” For the purpose of this guidance, these terms describe the same information and have been used interchangeably.

15.1 Study Design Overview

This randomized phase II study will assess the impact of tetanus pre-conditioning on migration among newly diagnosed GBM patients who have undergone definitive resection and completed standard temozolomide and radiation treatment, as well as the impact of tetanus pre-conditioning and basiliximab together on survival. After completing standard of care radiotherapy with concurrent temozolomide, patients will be randomized to 1 of 3 treatment arms:

- Group I will receive DC vaccinations with *unpulsed DC pre-conditioning* prior to the 4th vaccination;
- Group II will receive DC vaccinations with *Td toxoid pre-conditioning* prior to the 4th vaccination; and
- Group III will receive *basiliximab infusions* prior to the 1st and 2nd DC vaccinations along with Td toxoid pre-conditioning prior to the 4th vaccination.

A permuted block randomization algorithm using a 1:1:1 allocation ratio will be used to assign patients to a treatment arm. Randomization will be stratified by CMV status (positive, negative), with the assignment to arms I and II being double-blinded (See Sections 9.1.1 and 9.1.7 for further details).

The study was initially activated with Groups I and II. However, approximately 2 months the study's initial activation, the study has been amended to include Group III.

Once accrual to Groups I and II are complete, a decision will be made concerning the accrual of additional patients to the Groups I and II in order to assess the impact of Td toxoid pre-conditioning within subgroups defined by CMV status. Options include continued accrual to both strata, accrual to only one stratum, or termination of accrual. Details are provided in Section 15.8.

Per Section 9.1, the study has been amended to terminate randomization to Group III. Rationale is provided in Section 9.1. Though randomization to Group III has been terminated, the analyses proposed for Group III will still be done even though the power of planned analyses will be greatly reduced due to a sample size smaller than anticipated within Group III.

The study was closed to enrollment in April 2018 (Amendment 73). At the time the study was closed to new enrollment, a sufficient number of subjects have been enrolled to power the migration endpoint described in Section 15.9.3. An interim analysis of survival was initially planned after 35 patients were randomized to each Arm A and Arm B (Section 15.8). Survival analyses will still be conducted, but they may not be powered for the comparisons of survival described in Section 15.9.2. Exploratory immune analyses described in Section 15.7 will be conducted as planned.

15.2 Analysis Sets

Subject to the availability of data, all randomized patients will be included in all analyses of correlative and efficacy endpoints.

15.3 Patient Demographics and Other Baseline Characteristics

Summaries of clinical and socio-demographic characteristics will be generated for all enrolled patients, as well as a summary stratified by assigned treatment group for patients randomized. Categorical descriptors will be summarized using frequency distributions; whereas, interval variables will be summarized using percentiles, as well as means and standard deviations.

15.4 Treatments

A frequency distribution will be generated for the number of vaccines received among patients within each treatment arm.

15.5 Primary Objectives

This study has one key primary objective and three other primary objectives (See Section 8). The key primary objective is to assess the impact of Td pre-conditioning with or without basiliximab on survival.

Other primary objectives include an examination of the effect of pre-conditioning of the vaccine site with Td toxoid as opposed to unpulsed DCs at the time of the 4th vaccination on the migration of *CMV* pp65 RNA-pulsed DCs to site draining inguinal lymph nodes, as well as an assessment of the impact of Td pre-conditioning within subgroups of patients defined by *CMV* status (negative/positive).

15.5.1 Key Primary Objective: Overall Survival

The Kaplan-Meier estimator will be used to describe the survival within each of the 3 treatment arms. Median survival will be estimated within each arm, with 95% confidence intervals. OS will be defined as the time between randomization and death, or last follow-up if alive. Two pairwise one-tailed log-rank tests will be conducted to assess the impact of Td and/or basiliximab. One test will compare the survival experience of patients in the TD toxoid arm (Group II) and the unpulsed DC arm (Group I), and the other test will compare the survival experience within the basiliximab arm (Group III) and the unpulsed DC arm (Group I). An intent-to-treat philosophy will be followed in these analyses.

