9.1.7 Study Drug(s) Blinding

The Duke ICS Pharmacy will be responsible for the preparation of the Td and the saline used for the pre-conditioning done prior to the fourth vaccine. The unpulsed DCs used for pre-conditioning will be prepared in the DBTIP Laboratory and delivered to the ICS for the labeling and distribution of the blinded pre-conditioning drugs (i.e., Td, unpulsed DCs, and saline). Only those key personnel needed for the preparation and distribution of the pre-conditioning drugs will be unblinded (i.e., ICS pharmacy staff and DBTIP Lab study drug manufacturing personnel, as well as the statisticians). The patient and the remaining key personnel (including the PI and research nurses administering the pre-conditioning drugs) will be blinded to the pre-conditioning regimen. Emergency unblinding procedures are described in [13.3](#).

The administration of pre-conditioning agent (Td or unpulsed DCs) will be blinded for Groups I and II, however, the administration of the pre-conditioning agent (Td) and basiliximab for Group III will not be. Hence, patients and providers will know when a patient has been assigned to the third treatment group (please see randomization and blinding SOP [18.2](#) in appendices).

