15.5.3 Other Primary Objective: Survival Among *CMV* Positive Patients

To assess the impact of Td pre-conditioning on survival among patients who are *CMV* positive, an analysis similar to those described for the key primary objective will be generated within the subgroup of patients who are *CMV* positive. Specifically, the Kaplan-Meier estimator will be used to describe the survival among *CMV* positive patients within Groups I and II. Median survival will be estimated within each of these 2 treatment arms, with 95% confidence intervals.

OS will be defined as the time between randomization and death, or last follow-up if alive. A log-rank test will be conducted to assess the impact of pre-conditioning. An intent-to-treat philosophy will be followed in these analyses.

Subgroup analyses will be underpowered and descriptive unless a decision is made to continue accrual and treatment of CMV positive patients after the completion of accrual to Group III (See Section 15.8).

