15.6.1 Key Secondary Objective: PFS

The Kaplan-Meier estimator will be used to describe progression-free survival (PFS) within each arm. Median PFS will be estimated within each of the 3 treatment arms, with 95% confidence intervals. PFS will be defined as the time between randomization and initial failure (disease progression or death). If the patient remains alive without disease progression, PFS will be censored at the time of last follow-up. Two pairwise log-rank tests will be conducted to assess the impact of Td and/or basiliximab. One test will compare the PFS experience of patients in the TD toxoid arm (Group II) and the unpulsed DC arm (Group I), and the other test will compare the survival experience within the basiliximab arm (Group III) and the unpulsed DC arm (Group I). An intent-to-treat philosophy will be followed in these analyses.

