15.9.2 Key Primary Objective: Survival

The key primary goal of this study is to determine whether the addition of either Td pre-conditioning with vaccination #4 or basiliximab administration with vaccination #1 and #2 that is administered in conjunction with DC vaccination and temozolomide is worthy of investigation in a large phase III study. Two pairwise comparisons of survival are of primary interest: 1) Td Toxoid arm (Group II) versus Unpulsed DC arm (Group I), and; 2) Basiliximab arm (Group III) versus Unpulsed DC arm (Group I).

Though this phase II study is comparative, a false-positive rate of 0.15 will be used to test each hypothesis while maintaining reasonably high power[128-130]. This rate of false-positivity is used in lieu of a false positive rate of 0.2 as suggested in the literature in an attempt to partially adjust for there being multiple comparisons.

Within the ATTAC study, the median survival in the DC vaccine arm without pulsed DC pre-conditioning was approximately 12 months; whereas, within the Td pre-conditioning arm median survival was estimated to be approximately 36 months. Study results suggest a hazard ratio of approximately 0.33. Due to the small sample sizes in the ATTAC study, estimates are all associated with wide confidence intervals. Given these imprecise estimates and the potential for “regression to the mean” in this study replicating the ATTAC trial, we will target a smaller hazard ratio of 0.5 for a comparison of unpulsed DC (Group I) and Td (Group II). With pilot data not being available for the comparison of basiliximab (Group III) and unpulsed DC (Group I), we will also target a hazard ratio of 0.5 for that comparison.

For each pairwise comparison, a 1-tailed logrank test will be conducted at the 0.15 level of significance. In order that each comparison will have 90% power to detect a hazard ratio of 0.5, 45 deaths need to be observed within the two arms being compared[131].

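### Randomization is stratified by CMV serology, but the OS and PFS log-rank tests name no strata and no analysis estimates the design hazard ratio (minor improvement, not an error)

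*Combined protocol and SAP*

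**What the plan says.** Sections 9.1.1 and 15.1 describe permuted-block randomization with CMV serology as the stratification factor: "Randomization will be stratified by CMV status (positive, negative").

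Section 15.5.1 describes OS by Kaplan-Meier curves and per-arm medians with 95% confidence intervals. For testing, "Two pairwise one-tailed log-rank tests will be conducted to assess the impact of Td and/or basiliximab". Section 15.6.1 has the same structure for PFS: "Two pairwise log-rank tests will be conducted to assess the impact of Td and/or basiliximab". Neither section mentions strata, covariates, a Cox model or a hazard ratio.

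For this trial's survival comparisons, a hazard ratio appears only as a sample-size input. Section 15.9.2 says "we will target a smaller hazard ratio of 0.5 for a comparison of unpulsed DC (Group I) and Td (Group II"), and the same target recurs in Sections 15.9 and 15.9.4.

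CMV status enters the survival analyses only through separate comparisons within CMV-positive and CMV-negative patients (Sections 15.5.3, 15.5.4, 15.6.2 and 15.6.3). Section 15.5.3 limits their weight: "Subgroup analyses will be underpowered and descriptive unless a decision is made to continue accrual". Section 15.1 records closure to enrollment in April 2018 and says of the survival analyses that "they may not be powered for the comparisons of survival described in Section 15.9.2".

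**The concern.** There are two gaps. The first is that the pooled comparison does not use the factor on which the randomization was balanced. If CMV serology is prognostic, a test that ignores it runs below its nominal level and loses some power. The separate subgroup tests do not fill this gap, because they give neither a pooled stratified test nor a pooled effect estimate.

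The second is that no planned analysis estimates the quantity the trial was designed around. Section 15.9.2 uses Group II versus Group I to judge whether Td pre-conditioning merits a phase III study. It also frames the trial as a replication of ATTAC, whose result it summarises as a hazard ratio of about 0.33. Two medians and a p-value at one-sided 0.15 cannot be set directly against 0.33 or 0.5. A median may also not be reached: Section 7.3 gives the ATTAC Td arm only as more than 36.6 months. An interval for the effect matters more now that the survival comparison may be short of events.

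**Working it through.** **Inputs from the documents.** One-sided 0.15, 90% power, hazard ratio 0.5 and 45 deaths (15.9.2); medians of 12 and 24 months (15.9.2); 35 patients in each of Groups I and II (15.9); about 50% CMV positive (15.9.4); 29 months of accrual (15.9.1); 31 deaths expected at the interim (15.8).

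**The plan's own figure.** With 1:1 allocation the Schoenfeld formula gives

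deaths = (1.036 + 1.282)² / (0.25 × ln(0.5)²) = 5.373 / 0.1201 = 44.7, that is, 45.

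This matches the plan. It is an unstratified calculation, and stratifying leaves the formula unchanged.

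**Precision of a hazard ratio.** At 45 deaths SE(log HR) ≈ 2/√45 = 0.298, so the 95% interval is the estimate multiplied and divided by exp(1.96 × 0.298) = 1.79.

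- Observed HR 0.50: 95% CI about 0.28 to 0.90.
- The test is positive at or below exp(-1.036 × 0.298) = 0.73, where the 95% CI is about 0.41 to 1.32.
- At 31 deaths, power for HR 0.5 is Φ(0.693 × √31/2 - 1.036) = Φ(0.893) ≈ 0.81.

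**Plain versus CMV-stratified log-rank for OS, by simulation.** 40,000 trials per cell (SE about 0.2 points): exponential survival, overall Group I median 12 months, true treatment HR 0.5 (power) or 1 (size), uniform accrual over 29 months, 50% CMV positive, data cut at the stated number of deaths, critical value 1.036. Blocks of 4 within stratum are assumed. The hazard ratio between CMV strata is also assumed: 1, 0.67, 0.5 or 0.33, meaning no effect or a 1.5-, 2- or 3-fold effect.

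Each cell shows plain v stratified:

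| Group sizes, deaths | Measure | CMV HR 1 | 0.67 | 0.5 | 0.33 |
|---|---|---|---|---|---|
| 35 v 35, 45 | Power % | 89.5 v 89.1 | 89.0 v 89.1 | 88.3 v 89.3 | 85.6 v 89.2 |
| 35 v 35, 45 | Size | 0.152 v 0.152 | 0.149 v 0.153 | 0.144 v 0.153 | 0.129 v 0.154 |
| 35 v 35, 45 | Power %, both calibrated to size 0.15 | 89.4 v 88.9 | 89.1 v 88.8 | 88.8 v 89.0 | 87.7 v 88.9 |
| 25 v 25, 32 | Power % | 81.2 v 80.5 | 80.6 v 80.4 | 79.3 v 80.5 | 76.3 v 80.5 |
| 20 v 20, 25 | Power % | 74.6 v 73.9 | 74.1 v 73.8 | 72.9 v 73.9 | 69.5 v 74.0 |

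The number actually randomized is not stated, so the two smaller cases are assumptions. Calibrated power uses each test's own simulated null 85th percentile.

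At 35 v 35 the raw change is -0.4, +0.1, +1.0 and +3.6 points. The calibrated change is -0.5, -0.3, +0.2 and +1.2, so most of the raw gain is recovery from the plain test's conservatism. At 20 v 20 the calibrated change runs from -0.9 to +0.6.

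A second simulation (8,000 trials per cell, about 45 deaths) gave power of 88.7 v 88.2%, 88.5 v 88.7%, 88.1 v 89.1% and 85.6 v 89.0%, with plain size falling to 0.135 at threefold. The pattern is the same.

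**Which hazard ratio.** At 45 deaths and a true HR of 0.5, the median unstratified Cox estimate is 0.500, 0.506, 0.518 and 0.546 across the four CMV effects. The CMV-stratified estimate stays at 0.498 to 0.500.

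No PFS simulation was run. The documents give no design figures for PFS, so the extension to Section 15.6.1 rests on the same reasoning.

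**The case against.** The strongest reply is that nothing is broken. A plain log-rank test after stratified randomization is valid, it matches the formula behind the 45 deaths, and any departure from 0.15 is in the safe direction. The stratified test sits slightly above 0.15 in the simulations. The gain needs a CMV effect that the documents do not give, and with no such effect stratifying costs a little power. Table 1 declares median survival as the endpoint and Section 15.9.2 also states the alternative as medians, so the planned estimation fits the declared endpoint. The sections are silent about strata rather than ruling them out. Finally, a change of primary test now could look data-driven: enrollment is closed, and the unblinded staff listed in Section 9.1.7 are "ICS pharmacy staff and DBTIP Lab study drug manufacturing personnel, as well as the statisticians". Section 15.1 says "An interim analysis of survival was initially planned after 35 patients were randomized to each Arm A and Arm B", but the documents do not say whether it was run.

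Most of this stands and keeps the point minor. Stratifying removes no false-positive risk, and it offers little power unless CMV is strongly prognostic. The timing objection is real and shapes the fix. It does not remove the case for a pooled hazard ratio with its interval. Medians are not the scale of the 0.5 target, and the subgroup analyses do not supply that estimate.

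**Conclusion.** The point holds as a minor, low-cost improvement. No design figure is wrong and the plain test is valid. As written, the OS and PFS tests do not use the randomization stratum, and no survival analysis estimates the hazard ratio of 0.5 that the trial was sized for.

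At 35 v 35 and 45 deaths, the power effect of stratifying runs from -0.4 points (CMV not prognostic) to +3.6 (threefold), or -0.5 to +1.2 once both tests are calibrated. These figures rest on assumed CMV effects, exponential survival, 50% prevalence and blocks of 4. The firmer benefit is the effect estimate: a positive result can occur with a 95% interval as wide as 0.41 to 1.32, and a phase III decision should see that interval.

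**What to change.** In Sections 15.5.1 and 15.6.1, for Group II versus Group I, specify a log-rank test stratified by CMV serology as randomized, with a hazard ratio and confidence interval from a CMV-stratified Cox model. Leave the sidedness of each test and the 45-death target unchanged. Limit the change to this comparison, because with 9 patients in Group III (Section 9.1) its strata would be sparse.

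Date and document the change before anyone sees an OS or PFS comparison by arm. If that can no longer be assured, keep the plain log-rank test as primary and report the stratified test and hazard ratio as a sensitivity analysis, specified in a dated SAP change.

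The change needs no new patient, visit or assay. If CMV is not prognostic, the stratified test loses about 0.4 points of power at 35 v 35 and about 0.7 at 20 v 20. Its simulated size is 0.152 to 0.154 at 35 v 35 with 45 deaths and up to 0.156 at 20 v 20. The main cost is the risk that a late change of primary test looks data-driven, which the fallback avoids.
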